14.8 Missing data handling

Analyses will be conducted using a multiple imputation (MI) procedure. The imputed items are obtained from combining two components, a random component based on a normal distribution using the mean and standard deviation from the non-missing items from the variable being imputed, and a predicted component based on a multivariable regression model consisting of a set of variables with no missing data and the non-missing items from the variable being imputed. Multiple imputation does not attempt to estimate each missing value through simulated values but rather to represent a random sample of the missing values. This process results in valid statistical inferences that properly reflect the uncertainty due to missing values.

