14.6 Primary Analysis

To examine changes in the co-primary outcomes, the modified Lund-Kennedy score and the incidence of oral corticosteroid utilization per participant, a mixed effects longitudinal model will be fit that includes group (dupilumab, placebo) as a between participants factor and time (randomization through post-treatment period) as a categorical within participants factor plus their interaction term. Time is treated as categorical so that we can use the group-time interactions with the time main effect to estimate and test intent-to-treat (ITT) group differences at each time point, with 52 weeks as our primary ITT test. As randomization is stratified by site, site will also be included in the model. This mixed effects model allows incorporation of a random intercept term for each subject, different numbers of measurements (in case a visit is skipped), and the choice of appropriate variance-covariance structure. The mixed model will also permit identification of any significant changes in the post-treatment period from 52 to 64 weeks. This primary mixed model will incorporate all subject's randomized.

The primary objective will be assessed by testing this null hypothesis: treatment with Dupilumab post-surgery is equivalent to treatment with placebo post-surgery at 52-week end of treatment. The additional time point at 64 weeks is included in the model to ensure efficient evaluation of both co-primary outcomes at the EOT and 12 weeks after EOT. Significant changes between weeks 52 and 64 will be examined by linear contrast. We will test the following null hypotheses against two-sided alternatives:

- H₀₁: there is a lack of difference between the changes in mLK from baseline to 52 weeks and from baseline to 64 weeks for the untreated.
- H_{02} : there is a lack of difference between the changes in mLK from baseline to 52 weeks and from baseline to 64 weeks for the treated.
- H_{03} : the treatment effect dissipates between 52 and 64 weeks.

The primary estimand for the primary endpoint is the composite/treatment policy strategy. The intercurrent events will be handled as follows:

- Undergoing sinus surgery for AFRS: data after surgery will be assigned the worst possible score (composite strategy)
- Taking SCS or other rescue medications: data collected after use will be used in the analysis (treatment policy strategy)

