14.7 Secondary and Exploratory analyses

In a secondary analysis, a similar mixed model as described above will be fit that includes the subset of participants who are receiving treatment (dupilumab or placebo) for both nostrils. This model will incorporate nesting factors to identify repeated measures by subject and by nostril.

In an exploratory analysis, we will also compare the proportion of participants whose modified Lund- Kennedy score improved by greater than or equal to 2 units. For participants who undergo sinus surgery for AFRS prior to Week 52, non-responder imputation will be used. We will utilize a Chi-square or Fisher's exact test to examine if this proportion is significantly different by treatment group (dupilumab or placebo) at 52 weeks.

For the continuous secondary outcomes (e.g. SNOT-22 score, NPS, FEV1), a mixed effects longitudinal model will be fit that includes group (dupilumab, placebo), time (randomization through post-treatment period), and their interaction term in a similar fashioned as described for the primary outcome modified Lund-Kennedy score. For the secondary outcomes that compare the number of participants requiring rescue treatment and the number of adverse events (safety) over 52 weeks, similar mixed effects models will be fit but with consideration of a Poisson distribution (as opposed to normal distribution). The mixed effects models for both primary and secondary outcomes will permit the inclusion of any significant potential confounders.

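### Section 14.8 gives the random part of each imputed value the observed mean and SD of the variable, which is not regression multiple imputation, so its claim of valid inference does not follow

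*Combined protocol and SAP*

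**What the plan says.** Section 14.8 opens without exemption: "Analyses will be conducted using a multiple imputation (MI) procedure". Each imputed item combines two parts. One is "a random component based on a normal distribution using the mean and standard deviation from the non-missing items from the variable being imputed". The other is a prediction from "a multivariable regression model consisting of a set of variables with no missing data and the non-missing items from the variable being imputed". The combining operation is not given. The section closes: "This process results in valid statistical inferences that properly reflect the uncertainty due to missing values".

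Section 14.6 fits a mixed model to both co-primary outcomes, mLK and "the incidence of oral corticosteroid utilization per participant, a mixed effects longitudinal model will be fit". It says that this model allows "different numbers of measurements (in case a visit is skipped), and the choice of appropriate variance-covariance structure". Neither section says how the mixed model and the imputation relate. Visits after revision surgery have their own rule in Section 14.6 (worst possible score) and are not at issue here. Section 14.7 considers a Poisson distribution for the rescue-treatment and adverse-event outcomes, but no imputation model is given to match.

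**The concern.** In regression imputation the prediction already carries the mean, so the random term must be centred on zero and have the variance left over after the regression. Section 14.8 gives the random term the mean and SD of the observed values. This is a rule stated wrongly, not a detail left out, and nothing elsewhere in the documents repairs it.

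Two programmers could follow the section faithfully and report different Week 52 mLK differences. Some missing data must be expected. Section 4.7.2 discontinues participants from the study after missed visits or doses, whereas Section 10.1 keeps those who stop treatment enrolled and encourages further visits. Those two passages need reconciling in their own right.

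**Working it through.** **The plan's own figure.** Section 14.8 contains no number, so the anchor is Section 14.1: 66 per group, difference 2, SD 3.5, two-sided 0.05. SE = 3.5 × √(2/66) = 0.609; power = Φ(2/0.609 − 1.96) = Φ(1.32) = 0.907 (0.903 with the t distribution). The stated 90% reproduces and is not in question.

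**Inputs.** From the documents: 66 per arm, SD 3.5, a difference of 2 (Section 14.1), and the mLK range 0-12 (Section 5.2.1). Assumed: Week 52 means of 6 (placebo) and 4 (dupilumab), so a true difference of -2; Week 36 to Week 52 correlation 0.6; baseline correlation 0.3; missing 20%/10%, 10%/20% or 15%/15% (placebo/dupilumab).

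**The stated rule against the standard one.** Standard: prediction + N(0, (1 − R²)·SD²). Section 14.8: prediction combined with N(m, SD²), where m is the observed mean. With R² = 0.6² = 0.36, the stated variance is about 1/(1 − 0.36) = 1.56 times what it should be.

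**Bias by hand, missing at random within arm.** Let p be the missing fraction and μ the mean in each arm (P placebo, D dupilumab).

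- Observed mean m: at 20%/10%, (0.8×6 + 0.9×4)/1.7 = 4.94; at 10%/20%, (0.9×6 + 0.8×4)/1.7 = 5.06; at 15%/15%, 5.
- Parts averaged: shift = ½[p_D(m − μ_D) + p_P(μ_P − m)]. At 20%/10%: ½[0.10×0.94 + 0.20×1.06] = +0.15. At 10%/20%: ½[0.20×1.06 + 0.10×0.94] = +0.15. At 15%/15%: ½[0.15 + 0.15] = +0.15.
- Parts added: shift = (p_D − p_P)·m. This gives −0.10×4.94 = −0.49, +0.10×5.06 = +0.51, and 0.
- Mean dropped, marginal SD kept: shift 0.

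**Simulation** (1,200 trials per scenario, 20 imputations pooled by Rubin's rules, arm and baseline always in the imputation model):

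| Reading | 20%/10% | 10%/20% | 15%/15% |
|---|---|---|---|
| Nothing missing | -1.96 | -2.00 | -2.01 |
| Standard regression imputation | -1.97 | -2.00 | -2.01 |
| Averaged | -1.82 | -1.85 | -1.86 |
| Added | -2.46 | -1.51 | -2.02 |

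These agree with the hand calculation.

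- *Averaged:* coverage of the 95% interval is about 94-95%. In a separate run the mean SE was 0.592-0.595 against a sampling SD of 0.590-0.601, a ratio of 0.99-1.00.
- *Added:* 30-34% of imputed values exceed 12 in the two unequal scenarios.
- *Mean-zero with marginal SD:* estimates within 0.01 of the complete-data result; SE about 5-7% too wide (for example 0.68 against 0.65 for standard imputation); power 84-85% against 86-87%.

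A second simulation with different assumptions (correlation 0.5; missing 20%/20%, 30%/10% or 10%/30%) found standard regression imputation sound throughout: bias within 0.04 and coverage 94-97%.

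**Predictors (depends on the reading).** Suppose the requirement of no missing data excludes Week 36, and the log-odds of dropout rise by 1 per SD of the Week 36 score. Even with a correct residual term, the estimates are -1.85, -2.13 and -2.00 for the three missingness patterns. Against the same trials with nothing missing, the shifts are +0.15, -0.14 and 0.00. At 10%/5% and 5%/10% they are +0.08 and -0.07.

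**Non-normal outcomes (depends on the reading).** For a count with mean 3, the yearly number of steroid bursts quoted in Section 2, a raw normal draw is negative with probability Φ(−3/√3) = 4.2% if the variance is Poisson, and Φ(−3/√12) = 19.3% if it is overdispersed (variance 3 + 3² = 12). Averaging the draw with a prediction at the mean halves the SD, and these fall to 0.0% and 4.2%.

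**The case against.** The best defence is that Section 14.8 loosely describes what standard software does, and that the validity sentence speaks of multiple imputation in general. Standard software imputation would be valid for continuous data missing at random, and the reading nearest to it (mean-zero noise with the marginal SD) is almost harmless. That is a fair guess at intent. It does not rescue the text, which states the mean as well as the SD and attaches the validity claim to this process.

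Four stronger readings are tempting, and the documents do not support them.

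- *Averaging makes the standard error too small.* It is smaller than under standard imputation but accurate for the averaged estimator (ratio 0.99-1.00). The slight undercoverage comes mainly from the attenuation.
- *Earlier mLK visits are definitely excluded as predictors.* The same sentence also admits the non-missing items of the imputed variable, which could mean a participant's other observed mLK visits. Imputing visits in sequence would also remove the problem. Using only fully observed predictors is not invalid in itself.
- *Negative imputed counts would break the oral-corticosteroid co-primary analysis.* Section 14.6 names no Poisson model for it; Section 14.7 only considers one, for other outcomes. The 4.2% and 19.3% are for the raw draw before it is combined with a prediction. What stands is that one normal rule does not suit such outcomes.
- *Silence on parameter draws and pooling is an error.* It is an omission and is not counted here.

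**Conclusion.** The point holds as an error in the rule as written. The random component is mis-specified, and the claim of valid inference does not follow from it. For Week 52 mLK, the consequence is a shrinkage of about 0.15 if the parts are averaged, a shift of about 0.5 either way if they are added and the arms lose unequal numbers (unlikely in practice, given the off-scale values), or no bias with a standard error about 5-7% too wide if the mean is dropped. The predictor point is worth about 0.15 in either direction, only if earlier visits are excluded, dropout depends on Week 36 and rates differ by arm.

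A reader might infer that the rule favours dupilumab or that the trial's result will be wrong. Neither follows: the direction changes with the reading and with which arm loses more. All sizes rest on assumed dropout, means and visit correlations that the documents do not give.

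**What to change.** In Section 14.8, do one of the following.

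1. Make the likelihood-based mixed model of Section 14.6, which already accepts skipped visits, the primary mLK analysis, with multiple imputation as a sensitivity analysis.
2. Keep imputation as primary but replace the rule with sequential or fully conditional regression imputation. Predictors: arm, site, asthma status (a stratification factor in Section 4.1), baseline, and all mLK visits including those themselves imputed. Use mean-zero noise with the residual variance, parameter draws and Rubin's rules. Where the data allow, add treatment discontinuation and rescue use as predictors.

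In either case, state which analysis is primary, handle missing oral-corticosteroid and count outcomes with a count or logistic model according to how each endpoint is defined, and delete or re-justify the validity sentence. The number of imputations, rounding and predictive mean matching can be left to the trial statistician.

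The cost is plan wording and standard software, with no new data. It should be settled before unblinding.

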4.1 Overall Design

This is a multi-center, randomized, double-blinded, placebo-controlled, parallel group study to evaluate the efficacy of dupilumab 300mg administered subcutaneously (SC) every 2 weeks versus placebo in participants with AFRS following planned sinus surgery.

132 participants will be randomized to receive dupilumab 300mg SC or matching placebo while on a background of intranasal corticosteroid sprays twice daily. Patients will be stratified by study site and by baseline comorbid asthma status (yes vs no). ~25% of the randomized participants will have comorbid asthma.

Eligible participants will enter a screening/run-in period on twice daily nasal saline irrigations followed by INCS spray for 2-6 weeks prior to planned sinus surgery. Participants may be consented and enrolled at any time during this 2-6 week run-in period, provided the failure of appropriate medical therapy has been documented as outlined in the inclusion criteria. Eligible participants already on study background therapy for at least two weeks may be consented and enrolled during the pre-surgery period.

Both saline irrigations/INCS and sinus surgery will be completed per standard of care (SoC) and not according to the study protocol. Patients who continue to meet eligibility criteria following surgery will be randomized 1:1 before Visit 3 (Day 0) when they receive placebo or dupilumab 300mg SC every 2 weeks. Patients will receive a total of 26 doses of IMP, via either study

personnel (Visit 3-6 at W0, 12, 24 and 36) or home-administration (W2, 4, 6, 8, 10, 14, 16, 18, 20, 22, 26, 28, 30, 32, 34, 38, 40, 42, 44, 46, 48, 50) to maintain a 2-week treatment schedule. Patient compliance will be recorded via text messages the day of scheduled home administration, as well as monthly phone calls and collection of used syringes during scheduled study visits (Visit 4-7 at W12, 24, 36 and 52). An EOT visit will be conducted at Week 52 (Visit 7). Patients will then be monitored on daily saline irrigation and INCS spray for 12-weeks to evaluate potential disease recurrence after discontinuation of IMP. An EOS visit will be conducted at Week 64 (Visit 8).

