4.7 Randomization and blinding

Randomized participants will be stratified by enrollment site. Randomization will be assigned on a 1:1 basis to treatment group (dupilumab 300 mg every 2 weeks) or placebo. The study data team will prepare a randomization list based on computer-generated random numbers retrieved using a randomization procedure available in statistical packages such as SAS. Block randomization with varying block sizes will be employed to ensure that equal numbers of treatment and placebo participants occur within strata (site) and are balanced with respect to observed and unmeasured baseline factors.

This is a double-blind investigation. Patients, treating physicians and local study personnel will not be aware of cohort allocation.

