4.7.2 Treatment compliance

The study treatment provided for this study will be used only as directed in this Protocol. The IMP will either be administered at the study site during treatment visits (V3-6) or at home during weeks (2, 4, 6, 8, 10, 14, 16, 18, 20, 26, 28, 30, 32, 34, 38, 40, 42, 44, 46, 48, 50) to maintain a 2-week treatment schedule. Reminder text messages will be sent to all participants the day of a home-administration. Home-administration will be confirmed by recording of both confirmatory phone calls and used syringe collection.

If a home-administered IMP dose is missed and can be given within 7 days from the planned dose date, the IMP should be given. The patient's original schedule should be resumed. If the missed dose is not administered within 7 days, the IMP should not be given. This dose should be designated as a missed dose. IMP will then be given at the next date on the original schedule.

If a treatment visit needs to be rescheduled, the visit must be performed, and the IMP must be administered within 7 days of the original visit window. Investigators should make every effort to assure that no treatment visits are missed during the course of the study. A subject will be discontinued from the study if they miss either two consecutive study visits or IMP doses, or a total of three IMP doses throughout the study period. Any change from the dosing schedule will be recorded.

Investigators should also assure that participants are compliant and on a stable dose of the background INCS spray throughout study period. Any changes to background INCS spray will be recorded for subsequent analysis.

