14.1 Sample Size and Power analysis

A sample size of 66 participants per group achieves 90% power to detect a mean difference of 2 points on the modified Lund-Kennedy Endoscopic score at 52 weeks with a standard deviation of 3.5 and significance level of 0.05 using a two-tailed test. The clinically meaningful mean difference of 2 points and the standard deviation are based on previous study of mLK in a heterogeneous population with nasal polyps [5].

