- Discontinuing treatment: all data collected after discontinuation will be used in the analysis (treatment policy strategy)

We will examine the treatment effect in the subgroup of patients with unilateral disease by recording patients' time until next sinus surgery. We will investigate differences in this subgroup by examining the Kaplan-Meier curves and utilizing the log rank test of the difference between treated and non-treated. If there is a difference between survival times, we will use the Cox proportional hazard model to account for other relevant covariates such as disease severity.

The Bonferroni correction will be used to account for multiple testing and ensure Type-I error rate remains nominal.

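### Section 14.8's imputation makes no provision for whether a participant had stopped IMP, so it does not reliably target the treatment-policy effect set in section 14.6

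*Combined protocol and SAP*

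**What the plan says.** **Estimand.** Section 14.6 tests the group difference "with 52 weeks as our primary ITT test". For participants who stop IMP it says: "Discontinuing treatment: all data collected after discontinuation will be used in the analysis (treatment policy strategy". Scores after sinus surgery for AFRS are set to the worst value instead.

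**Missing scores.** Section 14.8 describes multiple imputation that combines a random draw, using the mean and SD of the observed values, with "a predicted component based on a multivariable regression model consisting of a set of variables with no missing data and the non-missing items" of the variable being imputed. It lists no predictors. It mentions neither treatment arm nor IMP status, and it plans no missing-data sensitivity analysis. The mixed model in section 14.6 has group, time, their interaction and site, but no term for being on or off IMP.

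**Follow-up after stopping.** Section 4.7.2 says: "A subject will be discontinued from the study if they miss either two consecutive study visits or IMP doses", and it adds a limit of three missed doses in total. Section 10.1 treats missed visits or doses as grounds for stopping study treatment. It keeps such participants enrolled, with a discontinuation visit within 8 weeks of the last IMP, encouragement to attend later visits, and continued data collection. Footnote a to Table 1 gives early stoppers the end-of-treatment procedures, which include endoscopy.

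**Wear-off.** Section 4.1 adds 12 weeks off drug "to evaluate potential disease recurrence after discontinuation of IMP". One hypothesis in section 14.6 concerns loss of the effect between Weeks 52 and 64.

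**The concern.** A treatment-policy effect at Week 52 needs the off-drug score of a participant who has stopped. Section 14.6 says what to do with such scores when they are collected. It does not say what to assume when they are missing, and that is left to section 14.8. There the donor information is every observed value, most of which will come from participants still taking IMP. Nothing commits the analyst to separating off-treatment from on-treatment scores.

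Missing Week-52 scores are likely to be concentrated among stoppers, because one section removes some of them from the study and another only encourages later attendance. If their scores worsen off drug and the imputation does not know that they stopped, part of the lost benefit is put back. The analysis would then miss the effect that the plan says it estimates, and no planned sensitivity analysis would reveal it.

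**Working it through.** **Inputs from the documents.** Section 14.1: "A sample size of 66 participants per group achieves 90% power to detect a mean difference of 2 points", with a "standard deviation of 3.5 and significance level of 0.05 using a two-tailed test". Section 4.7: "Randomization will be assigned on a 1:1 basis to treatment group".

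**Inputs assumed, because the documents give none.** q is the share of each arm that stops IMP. r is the share of stoppers who still have a Week-52 score. w is the share of the 2-point effect that a dupilumab stopper keeps at Week 52. q and r are taken as equal in the two arms.

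**Step 1: the plan's own figure.** The normal approximation gives 2 × (1.960 + 1.282)² × 3.5² / 2² ≈ 64.4, so 65 per group, with power 0.907 at 66. The noncentral t gives 66 per group and power 0.903. The stated sample size reproduces, and this point does not alter it.

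**Step 2: formulas for the expected Week-52 difference.**
- Treatment-policy truth: 2 × [(1 − q) + q·w].
- Imputation with arm but not IMP status, where missing scores follow the observed scores of their arm: 2 × [(1 − q) + q·r·w] / (1 − q + q·r).
- Imputation with neither arm nor status, where missing scores show no group difference: 2 × [(1 − q) + q·r·w].

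Example with q = 0.20, r = 0.50, w = 0. The truth is 2 × 0.80 = 1.600. With arm only, the result is 1.600 / 0.90 = 1.778, an excess of 0.178.

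**Step 3: results.**

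| q | r | w | Truth | Arm, no status | Excess | No arm, no status | Difference |
|---|---|---|---|---|---|---|---|
| 10% | 0 | 0 | 1.800 | 2.000 | +0.200 | 1.800 | 0 |
| 20% | 0 | 0 | 1.600 | 2.000 | +0.400 | 1.600 | 0 |
| 10% | 50% | 0 | 1.800 | 1.895 | +0.095 | 1.800 | 0 |
| 20% | 50% | 0 | 1.600 | 1.778 | +0.178 | 1.600 | 0 |
| 10% | 0 | 0.5 | 1.900 | 2.000 | +0.100 | 1.800 | −0.100 |
| 20% | 0 | 0.5 | 1.800 | 2.000 | +0.200 | 1.600 | −0.200 |
| 10% | 50% | 0.5 | 1.900 | 1.947 | +0.047 | 1.850 | −0.050 |
| 20% | 50% | 0.5 | 1.800 | 1.889 | +0.089 | 1.700 | −0.100 |
| 20% | 50% | 1 | 2.000 | 2.000 | 0 | 1.800 | −0.200 |

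The arm-only estimate equals the stay-on-drug value of 2.000 only when r = 0 or w = 1.

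**Step 4: the discontinuation-visit score.** Suppose this score enters the model, already shows the full loss, and correlates 0.6 with Week 52 at equal SDs (all assumptions). About 60% of the loss then carries into the imputed value. The worst case above falls from 0.40 to 0.40 × (1 − 0.6) = 0.16.

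**Step 5: does conditioning on status repair it?** Regression imputation was simulated with 1,000 trials, 66 per arm, SD 3.5, an assumed correlation of 0.5 with baseline, and w = 0.

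| q | r | Truth | Arm only | Arm and status |
|---|---|---|---|---|
| 20% | 50% | 1.60 | 1.76 | 1.59 |
| 20% | 25% | 1.60 | 1.90 | 1.59 |
| 30% | 50% | 1.40 | 1.67 | 1.41 |

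Conditioning on status recovers the target when some stoppers are observed. With r = 0 that model cannot be estimated, so a stated assumption is needed instead.

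**The case against.** **Silence is not a rule.** A reader might infer that section 14.8 prescribes imputation that ignores treatment status. It does not. It leaves the predictors unnamed, and dosing changes are recorded (section 4.7.2), so arm and stopping status could be among them. This stands. The fault is that nothing commits the analyst to the variables that the estimand needs.

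**Not simply an as-if-on-drug effect.** A reader might infer that the analysis estimates the effect had everyone stayed on IMP. Section 10.1 keeps stoppers in follow-up and section 14.6 uses their scores, so any retrieved off-drug scores make the estimate a blend. This stands. Stoppers who have sinus surgery receive the worst score and are not imputed as if on drug.

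**Direction is conditional.** A reader might infer that benefit is always overstated. That needs arm in the imputation model. Section 14.8's random component uses an overall mean and SD, and without arm the bias at full wear-off is about zero and otherwise towards no effect. This stands too. However, leaving arm out would sit badly with the group-by-time model in section 14.6, and agreement at one value of w would be a coincidence.

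**Full wear-off is an extreme.** Section 4.1 speaks only of possible recurrence after the scheduled end of treatment, and section 4.2 describes the same period as showing durability. The smaller figures, and the reduction from the discontinuation visit, are therefore part of the range.

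**Few stoppers to learn from.** At 10% to 20% stopping, about 7 to 13 of 66 per arm stop. If half return, about 3 to 7 per arm are observed. A separate model fitted to those alone would be fragile, which argues for a simple model with a fallback, not for leaving section 14.8 as it is.

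**Conclusion.** The point holds as a gap between estimand and imputation. Section 14.6 targets outcomes regardless of stopping, while neither section 14.8 nor the primary model makes provision for IMP status, and no sensitivity analysis tests the assumption.

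If arm is in the imputation model and the effect is fully lost after stopping, the Week-52 mLK estimate exceeds the treatment-policy effect. The excess is 0.20 to 0.40 points for 10% to 20% stopping with no stopper retrieved (10% to 20% of the planned 2 points), and about 0.10 to 0.18 with half retrieved. It is about half as large if half the effect is kept, zero without wear-off, and smaller if the discontinuation-visit score is used. If arm is omitted, the bias is about zero at full wear-off and otherwise towards no effect.

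Stopping, retrieval and wear-off rates are all assumptions. The documents support neither an unconditional claim of overstated benefit nor the claim that the plan estimates a pure stay-on-drug effect. The change should be made before unblinding.

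**What to change.** In section 14.8, for mLK:

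1. State that the imputation model includes treatment arm, IMP status at the visit (on or off, or time since stopping) and prior mLK scores, including the discontinuation visit. Scores missing after stopping are then informed by observed off-treatment scores in the same arm. Relax the present restriction to fully observed predictors, since interim mLK scores can themselves be missing.
2. Fix in advance the minimum number of retrieved stoppers per arm. If either arm falls below it, use a placebo-reference imputation for post-stop scores in both arms.
3. Add a reference-based or delta-adjusted sensitivity analysis, and report the imputation that ignores IMP status alongside.

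Separately, reconcile sections 4.7.2 and 10.1. One discontinues participants from the study after missed visits or doses. The other stops treatment only, keeps them enrolled and continues data collection. Which applies determines how many Week-52 scores are missing.

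The cost is plan wording and a modified imputation program. Dosing changes and mLK by visit are already recorded. The interval may be somewhat wider and the estimate less favourable to dupilumab.
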